2.4.4.2 Analysis of Hypoglycemia

Treatment-emergent hypoglycemia events will be tabulated separately from the AEs.

Event frequency and incidence of hypoglycemia events will be summarized by treatment for all reported hypoglycemia and per type of hypoglycemic event described in [Section 2.1.4.5](#) (ie, severe, documented symptomatic, asymptomatic, probable symptomatic, relative). Documented hypoglycemia (symptomatic or asymptomatic) will be also evaluated for the more stringent plasma glucose threshold of <3.0 mmol/L (<54 mg/dL), as well as for ≥ 3.0 and <3.9 mmol/L (≥ 54 and <70 mg/dL), and <3.9 mmol/L (<70 mg/dL). Frequency and percentage of participants with at least 1 hypoglycemia event will be summarized as well.

Event rate of hypoglycemia per participant year will be calculated by treatment using the total number of hypoglycemia events from all participants (denoted as n) divided by the total exposures from all participants expressed in years (ie, participant exposure in days divided by 365.25, denoted as t). Multiple events from an individual participant will all count. Event rates of hypoglycemia per participant year [all reported hypoglycemia, severe, documented symptomatic, asymptomatic, probable symptomatic, relative hypoglycemia, and documented hypoglycemia with plasma glucose <3.0 mmol/L (<54 mg/dL) as well as for ≥ 3.0 and <3.9 mmol/L (≥ 54 and <70 mg/dL), and <3.9 mmol/L (<70 mg/dL)] will be presented by treatment group for the whole on-treatment period.

A listing of participants for all severe hypoglycemia events reported on the specific eCRF “Hypoglycemic Event Information” page will be provided.

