| Sampling | | | | | | | | | | | | | | | collected just before their weekly injection (and at least 6 days after last IMP dose administration) for the predose serum concentration (C_{trough}) of efpeglenatide at selected clinical visits. For participants who consent, at least 1 additional postdose sample will be taken 3 days (±1 day) after administration of IMP, preferably between Week 8 and Week 12. See Section 8.5 . |
| Rescue therapy assessment | | Continuous assessment and recording during treatment periods | | | | | | | | | | | | | After randomization, the need of rescue therapy should be assessed by the Investigator via fasting SMPG performed by the participants and the central laboratory alerts received on FPG and on HbA1c (from Week 12 onwards). Participants must have an unscheduled in-person visit prior to rescue therapy initiation, with the assessments normally planned for EOT visit. See Section 6.1.2.2 . |

| Procedure | Screening (2 weeks) | Double-blind, placebo-controlled Core Treatment Period (30 weeks) | | | | | | | | | Double-blind, placebo-controlled Treatment Extension Period (26 weeks) | | | Post-treatment Follow-up Period (6 weeks) | Notes |
|---|--|---|------------|------------|------------|------------|-------------|-------------|-----------------|-------------|---|-------------|-------------|--|--|
| Visit | 1 | 2 | 3 | 4 | 5 | 6 | 7 | 8 | 9 | 10 | 11 | 12 | 13 | 14 | |
| | | R | | | | | 📞 | | | 📞 | | 📞 | EOT | EOS | |
| Week | -2 | 0 Baseline | 2 | 4 | 8 | 12 | 18 | 24 | 30 ^a | 36 | 43 | 50 | 56 | Last IMP+ 6 weeks | |
| Acceptable range (days) | -14 to -11 | 1 | 14 (±3) | 28 (±3) | 56 (±3) | 84 (±3) | 126 (±3) | 168 (±3) | 210 (±3) | 252 (±5) | 301 (±5) | 350 (±5) | 392 (±5) | 434 (±7) | |
| Concomitant medication review | Continuous assessment and recording throughout the study | | | | | | | | | | | | | | |
| AE/SAE recording | | | | | | | | | | | | | | | |
| Reporting hypoglycemia (symptoms, SMPG) | | | | | | | | | | | | | | | Hypoglycemia eCRF page must be filled in for all SMPG ≤70 mg/dL (3.9 mmol/L) and/or in case of symptoms suggesting hypoglycemia. |

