- **Asymptomatic hypoglycemia:** Asymptomatic hypoglycemia is an event not accompanied by typical symptoms of hypoglycemia but with a measured plasma glucose concentration less than or equal to 3.9 mmol/L (70 mg/dL).
- **Probable symptomatic hypoglycemia:** Probable symptomatic hypoglycemia is an event during which symptoms of hypoglycemia are not accompanied by a plasma glucose determination, but was presumably caused by a plasma glucose concentration less than or equal to 3.9 mmol/L (70 mg/dL); symptoms are treated with oral carbohydrate.
- **Relative hypoglycemia:** (recently termed “pseudo-hypoglycemia”) is an event during which the person with diabetes reports any of the typical symptoms of hypoglycemia, and interprets the symptoms as indicative of hypoglycemia, but with a measured plasma glucose concentration greater than 3.9 mmol/L (70 mg/dL).

In addition to the threshold of plasma glucose of ≤ 3.9 mmol/L (70 mg/dL), documented hypoglycemia with a measured plasma glucose concentration ≥ 3.0 and ≤ 3.9 mmol/L (≥ 54 and ≤ 70 mg/dL) and less than 3.0 mmol/L (< 54 mg/dL) will also be analyzed ([5](#)).

Hypoglycemic events will be evaluated regardless of the time of onset during the study and time of the day.

In addition, hypoglycemia events will be evaluated at the following time periods defined by time of the day:

- **Nocturnal hypoglycemia defined by time of the day:** any hypoglycemia of the above categories that occurs between 00:00 and 05:59, regardless of whether participant was awake or woke up because of the event.
- **Daytime hypoglycemia:** any hypoglycemia of the above categories that occurs between 06:00 and 23:59.

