| AEs | 
All AEs will be coded to a "LLT", "PT", "HLT", and "HLGT" and associated "SOC" using the version of MedDRA currently in use by the Sponsor at the time of database lock.
 
Adverse event incidence tables will be presented by primary SOC (sorted by internationally agreed order), HLGT, HLT and PT (sorted in alphabetical order) for each treatment group, showing the number (n) and percentage (%) of participants who experienced an AE.
 
The primary focus of AE reporting will be on TEAEs. Pretreatment and posttreatment AEs will be described separately.
 
Adverse event incidence tables will be provided by treatment group for all types of TEAEs: all TEAEs, all treatment-emergent SAEs, all TEAEs leading to permanent treatment discontinuation, and all TEAEs leading to death.
 
Tables will be presented for the "30-week core on-treatment period" and for the "whole on-treatment period including the 26-week controlled Treatment Extension Period".
 
AE, SAE, and AEs leading to death tables will be presented for the 30-week on-study period too.
 |
| Hypoglycemia | 
The number (%) of participants with at least 1 hypoglycemic event during the on-treatment period will be assessed per type of hypoglycemic event (see Section 8.2.5) and according to time of occurrence (nocturnal [ie, 00:00 to 05:59 am], daytime [06:00 to 23:59]). Documented hypoglycemia (symptomatic or asymptomatic) will be also evaluated for the more stringent SMPG threshold of <3.0 mmol/L (<54 mg/dL).
 
Summaries will be presented overall and by type of event for each treatment group.
 
The total number of events (per participant-years) will be computed and summarized overall and by type of event for each treatment group.
 
Similar summaries will be also provided for the 30-week core on-treatment period.
 |

| Endpoint | Statistical Analysis Methods |
|---------------------------------|--|
| Vital signs and laboratory data | For quantitative safety parameters based on central laboratory/reading measurements, descriptive statistics will be used to summarize results and changes from baseline values by visit and treatment group. |

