- **Severe hypoglycemia:** Severe hypoglycemia is an event requiring assistance of another person to actively administer carbohydrate, glucagon, or other resuscitative actions. These episodes may be associated with sufficient neuroglycopenia to induce seizure, unconsciousness, or coma. Plasma glucose measurements may not be available during such an event, but neurological recovery attributable to the restoration of plasma glucose to normal is considered sufficient evidence that the event was induced by a low plasma glucose concentration. The definition of severe symptomatic hypoglycemia includes all episodes in which neurological impairment was severe enough to prevent self-treatment and which were thus thought to place participants at risk for injury to themselves or others. Note that “requiring assistance of another person” means that the participant could not help himself or herself. Assisting a participant out of kindness, when assistance is not required, should not be considered a “requiring assistance” incident.

Severe hypoglycemia will be qualified as an SAE only if it fulfills SAE criteria. For example, events of seizure, unconsciousness, or coma must be reported as SAEs.

- **Documented symptomatic hypoglycemia:** Documented symptomatic hypoglycemia is an event during which typical symptoms of hypoglycemia are accompanied by a measured plasma glucose concentration less than or equal to 3.9 mmol/L (≤ 70 mg/dL). Clinical symptoms that are considered to result from a hypoglycemic episode are, eg, increased sweating, nervousness, asthenia/weakness, tremor, dizziness, increased appetite, palpitations, headache, sleep disorder, confusion, seizures, unconsciousness, or coma.
- **Asymptomatic hypoglycemia:** Asymptomatic hypoglycemia is an event not accompanied by typical symptoms of hypoglycemia but with a measured plasma glucose concentration less than or equal to 3.9 mmol/L (≤ 70 mg/dL).
- **Probable symptomatic hypoglycemia:** Probable symptomatic hypoglycemia is an event during which symptoms of hypoglycemia are not accompanied by a plasma glucose determination but was presumably caused by a plasma glucose concentration less than or equal to 3.9 mmol/L (≤ 70 mg/dL); symptoms treated with oral carbohydrate.

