- **Relative hypoglycemia:** (recently termed “pseudo-hypoglycemia”) is an event during which the person with diabetes reports any of the typical symptoms of hypoglycemia, and interprets the symptoms as indicative of hypoglycemia, but with a measured plasma glucose concentration greater than 3.9 mmol/L (> 70 mg/dL).

In addition to the threshold of plasma glucose of less than or equal to 3.9 mmol/L (≤ 70 mg/dL), documented symptomatic and asymptomatic hypoglycemic events with measured plasma glucose concentration ≥ 3.0 - < 3.9 mmol/L (≥ 54 - < 70 mg/dL) and less than 3.0 mmol/L (< 54 mg/dL) will also be analyzed.

Hypoglycemic events will be evaluated regardless of the time of onset during the study and time of the day.

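### The SAP's upper glucose band and its total leave out a reading of exactly 3.9 mmol/L (70 mg/dL), which protocol 8.2.5 and the SAP's own event definitions include

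*SAP*

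**What the plan says.** Protocol 8.2.5 sets documented symptomatic and asymptomatic hypoglycemia at or below 3.9 mmol/L (70 mg/dL) and relative hypoglycemia above it. It then adds two finer analyses of documented events: a band of "≥ 3.0 and ≤ 3.9 mmol/L (≥ 54 and ≤ 70 mg/dL" and events below 3.0 mmol/L (54 mg/dL). Table 7 in protocol 9.4.2 names only the lower cut-off, "for the more stringent SMPG threshold of <3.0 mmol/L (<54 mg/dL", but refers to 8.2.5 for the event types. The Schedule of Activities states "Hypoglycemia eCRF page must be filled in for all SMPG ≤70 mg/dL (3.9 mmol/L", and SAP Appendix B repeats this.

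SAP 2.1.4.6 keeps the inclusive definitions. A documented symptomatic event is one "accompanied by a measured plasma glucose concentration less than or equal to 3.9 mmol/L", and a relative event is one with symptoms "but with a measured plasma glucose concentration greater than 3.9 mmol/L". The band in the same section nevertheless reads "measured plasma glucose concentration ≥ 3.0 - < 3.9 mmol/L (≥ 54 - < 70 mg/dL". SAP 2.4.4.2 uses this strict band twice and adds a strict total each time: for incidence, "and <3.9 mmol/L (<70 mg/dL). Frequency and percentage of participants with at least 1 hypoglycemia event will be summarized as well", and for event rates, "and <3.9 mmol/L (<70 mg/dL)] will be presented by treatment group for the whole on-treatment period".

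SAP 1.5 is marked as not applicable. SAP 1.6 reports that the planned efficacy evaluations were dropped, that PK and ADA samples were not analyzed, and that the SAP was simplified. It does not mention hypoglycemia thresholds.

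**The concern.** The bound that defines a documented event and the bound that closes the band and total differ at one value, and that value is the threshold itself. A documented event there has no glucose row to go into. The glucose rows then need not add up to the documented events, and the SAP's band is not the one the protocol planned.

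Hypoglycemia incidence and rate are secondary safety endpoints, and after the early termination safety is one of the main things left to report. By-type event counts may allow boundary events to be inferred by subtraction. The number of participants with an event in the protocol's band cannot be recovered that way, because one participant can contribute to several rows.

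**Working it through.** The point depends on no sample-size, power or alpha figure, so there is no plan figure to reproduce. The check sets the ranges side by side and asks where a reading of 3.9 mmol/L (70 mg/dL), read as the paired threshold, is counted.

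| Category or row | Range, mmol/L (mg/dL) | Where stated | Counts 3.9 (70)? |
|---|---|---|---|
| Documented symptomatic or asymptomatic | ≤3.9 (≤70) | Protocol 8.2.5; SAP 2.1.4.6 | Yes |
| Relative | >3.9 (>70) | Protocol 8.2.5; SAP 2.1.4.6 | No |
| Lower cut-off | <3.0 (<54) | Protocol 8.2.5 and Table 7; SAP 2.1.4.6 and 2.4.4.2 | No |
| Band, protocol | ≥3.0 to ≤3.9 (≥54 to ≤70) | Protocol 8.2.5 | Yes |
| Band, SAP | ≥3.0 to <3.9 (≥54 to <70) | SAP 2.1.4.6 once; SAP 2.4.4.2 twice | No |
| Total, SAP only | <3.9 (<70) | SAP 2.4.4.2 twice | No |

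**Size of the gap.** In steps of 0.1 mmol/L the protocol band holds 10 values (3.0 to 3.9) and the SAP band 9 (3.0 to 3.8). In steps of 1 mg/dL the protocol band holds 70 − 54 + 1 = 17 values and the SAP band 69 − 54 + 1 = 16. The missing value is 3.9 mmol/L or 70 mg/dL. Taking the values ≤3.9 and removing those <3.0 and those from 3.0 to <3.9 leaves only 3.9.

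**Illustration, with assumed events** at 2.8, 3.4 and 3.9 mmol/L:
- Documented events (≤3.9): 3.
- SAP as written: 1 (<3.0) + 1 (band) = 2, and the <3.9 total is also 2.
- With the inclusive bound: 1 + 2 = 3, and the ≤3.9 total is 3.

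**Units.** Protocol Table 3 pairs 10 mmol/L with 180 mg/dL, a factor of 180 / 10 = 18.
- A reading of 70 mg/dL is 70 / 18 = 3.889 mmol/L. Unrounded, it meets <3.9 mmol/L but fails <70 mg/dL, so the strict bounds can classify it two ways. Under the inclusive bounds it is inside in both units.
- A reading of 3.9 mmol/L is 3.9 × 18 = 70.2 mg/dL. Unrounded, it meets ≤3.9 mmol/L but fails ≤70 mg/dL, so a governing unit is needed even after the bound is corrected.

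**The case against.** The strict rows may be intended. The SAP presents them as additional to the inclusive categories, uses the strict bound in all five places, and the rows are consistent with one another: below 3.0 plus 3.0 to <3.9 equals below 3.9. An inclusive total would largely repeat documented symptomatic plus asymptomatic events. The total has no protocol counterpart, so it cannot depart from the protocol. SAP 1.5 covers changes to the protocol's statistical section, whereas the band stands in 8.2.5, an assessment section. Finally, a 70 mg/dL reading analyzed unrounded in mmol/L would fall inside the SAP's rows.

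Much of this stands. The total conflicts only with the SAP's own definitions; only the band departs from the protocol. SAP 1.5 is not shown to be wrong, and the place to declare the change is SAP 1.6. The unit point stands too, but it shows that the strict bounds disagree between units, which is a further reason to settle them.

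Intent does not remove the problem. Consistency among the strict rows does not reconcile them with the inclusive definition in SAP 2.1.4.6, where a single sentence gives the overall threshold as ≤3.9 and the band as ending at <3.9. Nor does it supply the band that protocol 8.2.5 says will be analyzed. A deliberate strict cut-off would need declaring, and it is not declared.

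**Conclusion.** The concern holds and is minor. Followed as written, the SAP applies a different upper bound from protocol 8.2.5 for the band, and from its own event definitions for both the band and the total. Two of the three glucose cut-offs are affected, in both the incidence and the rate summaries, at one boundary value.

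No event is lost from the report, since the all-reported and by-type summaries still count it. The 3.0 mmol/L (54 mg/dL) cut-off is the same throughout. SAP 2.4.4 makes the safety analysis descriptive, so no hypothesis test is affected.

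The conclusion takes 3.9 mmol/L and 70 mg/dL as the paired threshold that the documents present. How many events or participants sit there cannot be quantified, because the documents give neither event counts nor a glucose distribution.

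**What to change.** Change the band to ≥3.0 and ≤3.9 mmol/L (≥54 and ≤70 mg/dL) once in SAP 2.1.4.6 and twice in SAP 2.4.4.2. Change both totals in SAP 2.4.4.2 to ≤3.9 mmol/L (≤70 mg/dL). State which unit governs classification and how converted values are rounded. The <3.0 row and the band then divide all documented events with nothing left over.

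If a strict cut-off below 3.9 mmol/L is wanted, keep it as an additional row and declare it in SAP 1.6 as a difference from protocol 8.2.5.

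The cost is five thresholds in the SAP text, a sentence on units and rounding, and the matching change to the derivation. No new data are needed.

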6.1.2 Noninvestigational medicinal products

6.1.2.1 *Background medication*

Lantus

Lantus is the only background therapy provided by the Sponsor. The appropriate number of kits will be dispensed for the period until the next dispensing visit (please refer to the SoA [Section 1.3](#)). Lantus will be provided until the end of study even in case of premature end of treatment for patients attending the safety follow-up visits. Storage conditions and use-by-end date (when required by country regulations) are part of the label text.

- Formulation: Lantus will be supplied as a sterile, nonpyrogenic, clear, colorless solution in the marketed Lantus SoloStar prefilled (disposable) pen (insulin glargine 100 U/mL solution for SC injection). Each Lantus SoloStar contains in total 300 units of insulin glargine (3.0 mL of 100 units/mL insulin glargine solution). The pen allows dose setting in the range of 1 to 80 units with minimum of 1 unit increment. Lantus must not be diluted or mixed with any other insulin or solution.
- Route of administration: SC.
- Dose regimen: Injections should be administered once daily at any time of the day, but at the same time every day SC to the abdomen, thigh, or upper arm. Within these regions, the sites of injection should be changed (rotated) at each administration to prevent skin reactions.

Lantus starting dose at beginning of Treatment Period

- At randomization, the prestudy dose of basal insulin (glargine 100 U/mL) should be converted to an equivalent dose of Lantus on a 1:1 unit basis. If HbA1c at screening is $\leq 8.0\%$, the daily dose of Lantus should be reduced by 20% at randomization in order to avoid hypoglycemia when the participant starts the combination therapy with IMP.
- The starting dose of Lantus can be further adjusted as per Investigator's discretion based on most recent fasting SMPG values and HbA1c value before randomization.

Lantus dose adjustment

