- After randomization, the Lantus dose should be kept stable within the first 8 weeks after addition of study treatment unless a dose adjustment is required in case of, eg, repeated hypoglycemia. After Week 8 (Visit 5), the Lantus dose should be adjusted according to the algorithm ([Table 3](#)) or local titration standards as needed based on the median of the 3 most recent fasting (prebreakfast) SMPG values measured by the participant using glucose meter and accessories supplied by the Sponsor. The SMPG values and all Lantus dose adjustments are to be documented in the patient diary.
- **Daily fasting (prebreakfast) SMPG** measurements are required during first 8 weeks after randomization, when the study treatment is added and increasingly contributing to the glycemic control. After Week 8 (Visit 5), three fasting (prebreakfast) SMPG values per week are mandatory prior to each visit (these may include the day of the visit). During the other weeks fasting SMPG values are to be measured at the discretion of the Investigator.

Table 3 - Recommended Lantus dose adjustment algorithm

| Median of the 3 most recent fasting (prebreakfast) SMPG values | Lantus dose adjustments (U/day)* |
|---|--|
| ≥10 mmol/L (≥180 mg/dL) | +8 |
| ≥7.8 mmol/L to <10.0 mmol/L (≥140 to <180 mg/dL) | +6 |
| ≥6.7 to <7.8 mmol/L (≥120 and <140 mg/dL) | +4 |
| >5.6 to <6.7 mmol/L (>100 and <120 mg/dL) | +2 |
| Glycemic target: ≥4.4 to 5.6 mmol/L (≥80 to 100 mg/dL), inclusive | No change |
| ≥3.3 and <4.4 mmol/L (≥60 to <80 mg/dL) | -2 |
| <3.3 mmol/L (<60 mg/dL) or occurrence of 2 (or more) symptomatic hypoglycemic episodes or one severe hypoglycemic episode (requiring assistance) in the preceding week. | - 3 to -4 or at the discretion of the Investigator or medically qualified designee** |

* Dose adjustment should not be done more often than every 3 to 4 days.

** in case of SU background treatment, SU reduction or discontinuation might also be considered

SMPG: self- monitored plasma glucose, SU: sulfonylurea

In case of any concerns with the treatment, additional unscheduled visits (telephone contact or clinic visits) may be arranged as needed.

Oral antidiabetic drug(s) (OAD[s])

- Route of administration: Oral.

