2.4.4 Analyses of safety data

The summary of safety results will be presented by treatment group on the “whole on-treatment period” as defined in [Section 2.1.4](#).

General common rules

All safety analyses will be performed on the safety population as defined in [Section 2.3.2](#), unless otherwise specified, using the following common rules:

- Safety data in participants who do not belong to the safety population (eg, treated but not randomized) will be listed separately

- The potentially clinically significant abnormality (PCSA) values are defined as abnormal values considered medically important by the Sponsor according to predefined criteria/thresholds based on literature review and defined by the Sponsor for clinical laboratory tests, vital signs, and ECG (PCSA version 3 date dated 21 May 2014 effective date 24 May 2014 [[Appendix A](#)])
 - PCSA criteria will determine which participants had at least 1 PCSA during the whole on-treatment period, taking into account all evaluations performed during the whole on-treatment period, including nonscheduled or repeated evaluations. The number of all such participants will be the numerator for the whole on-treatment period PCSA percentage.
 - The treatment-emergent PCSA denominator by group for a given parameter will be based on the number of participants assessed for that given parameter in the whole on-treatment period by treatment group on the safety population.
- The analysis of the safety variables will be descriptive, and no systematic testing is planned.

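### Hypoglycemia is summarised over the whole on-treatment period only, so an early between-arm difference while Lantus is held stable can be diluted by the later titration phase

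*SAP*

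**What the plan says.** **Time window.** SAP 2.4.4 sets the general rule: "The summary of safety results will be presented by treatment group" on the whole on-treatment period. For hypoglycemia this runs from first injection to 7 days after the last (SAP 2.1.4). SAP 2.4.4.2 repeats the window for the event rates, which "will be presented by treatment group for the whole on-treatment period". The rate is the total number of events "divided by the total exposures from all participants expressed in years". Rates are given for all reported events, five event types and three glucose categories. In addition, "Frequency and percentage of participants with at least 1 hypoglycemia event will be summarized as well", and severe events are listed.

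**Insulin and monitoring.** Protocol 6.1.2.1 divides the treatment period at Week 8.

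- Before: "After randomization, the Lantus dose should be kept stable within the first 8 weeks after addition of study treatment", with an exception where adjustment is required, for example after repeated hypoglycemia. Fasting self-monitoring is daily. Study drug is escalated to its assigned dose by Week 4 (Protocol 6.1, Table 2).
- After: "After Week 8 (Visit 5), the Lantus dose should be adjusted according to the algorithm" or local titration standards. Three fasting values are mandatory in the week before each visit; in other weeks measurement is at the investigator's discretion.

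Where screening HbA1c is 8.0% or lower, the daily Lantus dose is to be "reduced by 20% at randomization in order to avoid hypoglycemia when the participant starts the combination therapy with IMP".

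**Second window in the protocol.** Protocol 9.4.2, Table 7, says of hypoglycemia: "Similar summaries will be also provided for the 30-week core on-treatment period". SAP 2.1.4 defines that period but SAP 2.4.4.2 assigns no summary to it. SAP 1.5 reports no modifications to the protocol's statistical section. SAP 1.6 describes a simplified plan after early termination and names only efficacy, PK and ADA as not performed or not analysed.

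**The concern.** Incidence and rate of hypoglycemia are secondary safety endpoints (Protocol 3, Table 1), and after early termination SAP 2.4 puts safety among the main remaining outputs. A natural question for a drug added to insulin is what happens while the drug is being introduced and insulin is meant to be held. The protocol's own precaution at randomization shows that this risk was foreseen.

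The planned table cannot show that phase separately. Events from the first 8 weeks are mixed with events from the titration phase. There, blinded adjustment towards a fasting target could raise insulin more on placebo than on efpeglenatide, so the between-arm contrast need not be the same in the two phases. Required glucose measurement also falls at Week 8, so detection of asymptomatic and threshold-defined events changes at the same point. The weight of each phase in the pooled figure depends on how much follow-up the early termination left.

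**Working it through.** **Plan's own figure.** Neither document states a hypoglycemia rate, ratio or precision, so there is nothing to reproduce on this point. The only design calculation is the HbA1c power (100 per arm, SD 1.1%). It reproduces at 89.5% and 97.1% against the stated 89% and 96%, and has no bearing here.

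**Inputs.** From the documents: the phase boundary at 8 weeks and the planned treatment length of 56 weeks. Assumed: placebo rate 3.0 per participant-year to Week 8 and 4.0 after; early rate ratio 1.5, so efpeglenatide 4.5; late rate ratio 1.0 (efpeglenatide 4.0) or 0.85 (efpeglenatide 3.4); equal follow-up of w weeks in both arms, with w = 20, 30 or 40.

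**Formula.** Pooled rate = [8 × early rate + (w − 8) × late rate] / w. The divisor w cancels in the ratio, so the columns below show the bracketed sums.

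| w | Placebo | Efpeglenatide, late ratio 1.0 | Pooled ratio | Efpeglenatide, late ratio 0.85 | Pooled ratio |
|---|---|---|---|---|---|
| 20 | 24 + 48 = 72 | 36 + 48 = 84 | 1.17 | 36 + 40.8 = 76.8 | 1.07 |
| 30 | 24 + 88 = 112 | 36 + 88 = 124 | 1.11 | 36 + 74.8 = 110.8 | 0.99 |
| 40 | 24 + 128 = 152 | 36 + 128 = 164 | 1.08 | 36 + 108.8 = 144.8 | 0.95 |

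**What cancellation would need.** Let r be the early ratio and k the placebo late rate divided by the placebo early rate. The pooled ratio equals 1 when the late ratio is 1 − 8(r − 1)/[(w − 8)k]. With r = 1.5 and k = 4/3 this is 0.75 at 20 weeks, 0.86 at 30 and 0.91 at 40. It is below 1 whenever r exceeds 1, so cancellation always needs a reversed contrast in the later phase.

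**Full planned length.** Weeks 0 to 8 are 8/56 = 14.3% of planned treatment. With r = 2 and equal late rates, the 56-week pooled ratio is (8 × 2 + 48)/56 = 1.14 for k = 1, and (16 + 72)/(8 + 72) = 1.10 for k = 1.5. To reach 1.00 the late ratio would have to be 0.83 or 0.89 respectively.

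**The 30-week core window.** It dilutes less: with r = 2 and equal late rates the pooled ratio is (16 + 22)/30 = 1.27 for k = 1, and (16 + 33)/(8 + 33) = 1.20 for k = 1.5. It still mixes the two phases, since Weeks 0 to 8 are 8/30 = 26.7% of it.

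**Information in the early phase.** At the planned 100 per arm, Weeks 0 to 8 supply at most 100 × 56/365.25 = 15.3 participant-years per arm.

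**The case against.** The protocol endpoints are participants with at least one event, and events per participant-year, during the treatment period. SAP 2.4.4.2 delivers both. A net rate under the insulin rules actually in force is a legitimate safety summary. The plan is a simplified one for a synopsis report, safety is descriptive, and no test or primary conclusion depends on this table. All of that stands.

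Stronger readings are tempting, but the documents do not support them:

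- **An early excess disappears in the pooled rate.** No rates are given, and cancellation needs a late contrast in the opposite direction. With equal late rates the result is dilution. Protocol 2.2 describes the class as generally low-risk for hypoglycemia.
- **Insulin is frozen and then driven to one target.** Adjustment is allowed before Week 8 when required. The starting dose may be cut by 20% or further adjusted at the investigator's discretion, and local titration standards may replace the algorithm. Weeks 0 to 8 are therefore not a pure unchanged-insulin phase, and the two higher-dose arms are still escalating for part of them.
- **There is only one rate.** There are nine rate categories plus incidence and a severe-event listing. Only the time window is single.
- **The change in self-monitoring biases the comparison of arms.** The schedule is the same in every arm. It does limit comparison of one phase with the other.

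The missing 30-week core summary is a separate discrepancy. Restoring it would not isolate the early phase.

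None of this gives the reader a view of hypoglycemia during the add-on phase. The severe-event listing covers one event type and gives no rate by phase.

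**Conclusion.** The point holds as a cheap improvement to descriptive safety reporting. It is not an error in the pooled rate. Every hypoglycemia summary in the SAP uses a window that spans both insulin phases, and such a window can dilute an early difference between arms.

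How much is unknown. Under the assumed rates, an early ratio of 1.5 becomes 1.08 to 1.17 with no later difference, and 0.95 to 1.07 with a late ratio of 0.85. These figures rest on assumed rates and equal follow-up in the arms. A reader might infer that the trial's hypoglycemia result will be misleading; the documents establish only that the planned table could not show whether the phases differ.

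The unrecorded loss of the 30-week core hypoglycemia summary is a documented mismatch between protocol and SAP and needs its own correction.

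**What to change.** In SAP 2.4.4.2, keep the pooled rows and add n (%), number of events, exposure and rate by arm for:

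- (a) first injection to the Week 8 visit (Day 56 if that visit is missing), or to the end of the on-treatment period if earlier;
- (b) after Week 8 to the end of the on-treatment period, among participants still on treatment.

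Do this at least for all reported, severe, documented symptomatic and below 3.0 mmol/L events. Exposure should be counted within each phase, so that events and exposure in (a) and (b) add up to the pooled rows. State that arms are to be compared within a phase and not across phases, because self-monitoring intensity changes at Week 8, and that (b) describes only those who remained on treatment.

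Separately, restore the 30-week core hypoglycemia summary from Protocol 9.4.2, or record in SAP 1.6 that it was dropped and why.

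The cost is a few more descriptive rows in a simplified plan. Event onset dates and dosing dates are already collected. Rows for rare types, such as severe events, will be sparse. No insulin or other clinical rule changes.
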